12.10. Pharmacokinetic Analysis

12.10.1. Pharmacokinetic Parameters

As appropriate and where possible, the following PK parameters will be assessed for verinurad, M1, M8, allopurinol, and oxypurinol using plasma concentrations.

AUC	Area under plasma concentration-time curve from time zero to infinity
AUC(0-t)	Area under the plasma concentration-time curve from time zero to time of last quantifiable concentration
C _{max}	Maximum observed plasma concentration
t _{max}	Time to reach maximum observed plasma concentration
t _{lag}	Time delay between drug administration and the first observed concentration in plasma
t _{1/2λz}	Half-life associated with terminal slope (λ _z) of a semi-logarithmic concentration-time curve
t _{last}	Time of last quantifiable plasma concentration
CL/F	Apparent total body clearance of drug from plasma after extravascular administration (parent drug)
V _z /F	Apparent volume of distribution during the terminal phase after extravascular administration (parent drug)
V _{ss} /F	Apparent volume of distribution at steady state
MRT	Mean residence time of the unchanged drug in the systemic circulation from zero to infinity

The following diagnostic parameters for plasma PK analysis will be listed, but not summarised:

t lower	Start of exponential fit
t upper	End of exponential fit
λ _z N	Number of data points included in the log-linear regression analysis
Rs _q -adj	Regression coefficient adjusted for λ _z N, Goodness-of-fit statistic for calculation of λ _z
%AUC _{extr}	Percentage of AUC obtained by extrapolating the area under the plasma concentration-time curve from the time of the last quantifiable concentration to infinity
λ _z	Terminal elimination rate constant

Additional PK parameters may be determined where appropriate.

12.10.2. Derivation of Pharmacokinetic Parameters

The PK analyses of the plasma concentration data for verinurad, M1, M8, allopurinol, and oxypurinol will be performed by Covance Clinical Pharmacokinetic Alliance (CPKA), on behalf of AstraZeneca Research and Development (R&D).

PK parameters will be derived using non-compartmental methods with Phoenix[®] WinNonlin[®] Version 8.1, or higher. All descriptive and inferential statistical analyses will be performed using SAS[®] Version 9.4, or higher.

PK analysis will, where possible, be carried out using actual times recorded in the raw data. If actual times are missing, nominal times will be used.

Plasma concentrations which are NQ prior to the first quantifiable concentration will be set to a value of zero. After the first quantifiable concentration, any NQ plasma concentrations will be set to missing for all concentration profiles. Where 2 or more consecutive concentrations are NQ at the end of a profile, the profile will be deemed to have terminated and therefore any further quantifiable concentrations will be set to missing for the calculation of the PK parameters unless it is considered to be a true characteristic of the profile of the drug.

If an entire concentration-time profile is NQ, the profile will be excluded from the PK analysis.

C_{max}, t_{max}, t_{lag}, t_{last}, t_{lower} and t_{upper} will be taken directly from the plasma concentration-time profile.

Terminal elimination half-life, calculated as $(\ln 2)/\lambda_z$, will be estimated by log-linear least squares regression of the terminal part of the concentration-time curve. For the determination of λ_z , the start of the terminal elimination phase for each subject will be defined by visual inspection and will be the first point at which there is no systematic deviation from the log-linear decline in plasma concentrations (t_{lower}). The last point (t_{upper}) will be the time of the last quantifiable plasma concentration. A minimum of 3 data points will be used in calculating λ_z , and the duration of time over which λ_z is recommended to be at least 3 times the subsequently estimated terminal half-life. Where an elimination half-life is estimated over less than 3 times the subsequently estimated terminal half-life, it will be flagged and commented upon in the study report and agreement reached with the Sponsor regarding exclusion of λ_z and dependent parameters (t_{1/2}, λ_z , AUC, CL/F, MRT, V_z/F and V_{ss}/F) from the corresponding statistical analyses.

The R_{sq}-adj value will also be calculated to show the goodness-of-fit of the choice of datapoints taking into consideration the number of points used in the estimation. Where the R_{sq}-adj value is <0.8 it will be flagged and commented upon in the CSR and agreement reached with the Sponsor regarding exclusion of λ_z and dependent parameters from the statistical analyses.

AUC values (including AUC and AUC_{0-t}) will be calculated using the linear trapezoidal method when concentrations are increasing and the logarithmic trapezoidal method when concentrations are decreasing (linear up, log down method). AUC is estimated by $AUC_{0-t} + C_{last}/\lambda_z$ where C_{last} is the observed last quantifiable drug concentration. The AUC values where the percentage extrapolation is greater than 20% and any parameters dependent on AUC will be flagged in the data listings and agreement reached with the Sponsor on whether exclusions from the summary or formal statistics are required.

The minimum requirement for the calculation of AUC will be the inclusion of at least 3 consecutive plasma concentrations above the lower limit of quantification (LLOQ), with at least 1 of these concentrations following C_{max} .

Apparent clearance (CL/F) will be determined from the ratio of dose/AUC. Apparent volume of distribution based on the terminal phase (V_z/F) will be determined from the ratio of dose/ $\lambda_z * AUC$. V_{ss}/F will be determined by multiplying CL/F by MRT.

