5.2.1.3. Clinical Pharmacokinetics

Following administration of verinurad as an extended-release capsule formulation (ER8), C_{max} occurred 4 hours after dosing. Food did not affect verinurad exposure except for a 2-hour increase in time to maximum plasma concentration (t_{max}). The degree of protein binding of verinurad in human plasma was 97%. Glucuronidation is the major metabolic pathway of verinurad with oxidation as the minor pathway. The major metabolites observed in humans after oral verinurad dosing are the acyl glucuronides M1 and M8 which are renally cleared. The amount of verinurad in urine is small (<2% of given dose). The terminal half-life ($t_{1/2}$) of verinurad was 13 hours in subjects with normal renal function and 21 hours in those with moderate renal impairment. The exposure (area under the concentration-time curve [AUC] and C_{max}) of verinurad increased in a dose-proportional manner and the accumulation was minimal after once daily dosing. Subjects with an estimated glomerular filtration rate (eGFR) of 45 and 60 $\text{mL}/\text{min}/1.73\text{m}^2$ are predicted to have a 1.4 and 1.2-fold higher verinurad exposure, respectively, compared to those with normal renal function (eGFR of 90 $\text{mL}/\text{min}/1.73\text{m}^2$). Asian subjects are

predicted to have about 44% higher exposure compared to non-Asians after accounting for differences in renal function and body weight.

Further information on pharmacokinetics (PK) findings (including PK parameters of the verinurad immediate-release [IR] formulation) is available in the IB [15].

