5.3.2. Overall Study Design

This study will be a single-centre, randomised, placebo-controlled, double-blind, 3-period, cross-over Phase I study to assess the effect on the QTcF interval of a single oral dose of verinurad 24 mg ER8 formulation (therapeutic exposure) or verinurad 40 mg IR formulation (supra-therapeutic exposure), each in combination with allopurinol 300 mg, compared to placebo in healthy subjects.

There are 3 study treatments (see also [Table 9-3](#)):

- Treatment A: Verinurad 24 mg ER8 formulation co-administered with 300 mg allopurinol
- Treatment B: Verinurad 40 mg IR formulation co-administered with 300 mg allopurinol
- Treatment C: Matched placebos for both verinurad and allopurinol

All subjects will receive a single dose of all 3 treatments (A, B, and C) in a cross-over design with wash-out periods of at least 7 days between each study dose administration. Subjects will be randomised to the treatment sequence (ABC, BCA, CAB, etc.) using

William's Latin square. The treatments will be administered in a double-blind manner after an overnight fast of at least 10 hours.

There will be 5 visits to the study centre, including 3 visits that are residential. The study will comprise the following periods and visits:

- A Screening Period of maximum 28 days (Visit 1);
- Three treatment periods of 3 days each, during which subjects will be resident at the study centre from the morning of the day before administration of the study dose (check-in, Day -1) until discharge 2 days after study dose administration (check-out, Day 3; Visits 2 to 4);
- Wash-out periods of at least 7 days between each study dose administration;
- A final visit within 7 to 10 days after the last study dose administration (Follow-up Visit; Visit 5).

A total of 24 subjects are planned to be randomised to achieve at least 20 evaluable subjects.

The study design is deemed appropriate for conduct in healthy volunteers during COVID-19 pandemic.

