6.2. Secondary Objectives

Table 6-2 Secondary Objectives and Outcome Measures

Secondary Objectives	Outcome Measures
To investigate the effect of verinurad given either as a 24 mg ER8 formulation (therapeutic exposure) or a 40 mg IR formulation (supra-therapeutic exposure), both in combination with allopurinol 300 mg, on HR and additional dECG variables (PR, QRS, QT and RR).	
 Baseline-corrected and placebo-adjusted dECG parameters (ΔHR, $\Delta\Delta\text{HR}$, ΔRR interval, $\Delta\Delta\text{RR}$ interval, ΔPR interval, $\Delta\Delta\text{PR}$ interval, ΔQRS interval, $\Delta\Delta\text{QRS}$ interval, ΔQT interval, $\Delta\Delta\text{QT}$ interval, ΔQTcF interval, $\Delta\Delta\text{QTcF}$ interval). Parameters for this outcome measure are the dECG variables HR, RR, PR, QRS, QT and QTcF.
To assess the PK of verinurad and its metabolites (M1 and M8) and allopurinol and its metabolite (oxypurinol) in healthy subjects.	
 As appropriate and where possible, the following PK parameters will be assessed for verinurad, M1, M8, allopurinol, and oxypurinol: AUC, AUC_{0-t}, C_{max}, t_{max}, t_{lag}, $t_{1/2\lambda z}$, t_{last}, CL/F, V_z/F, V_{ss}/F and MRT. Plasma concentration-time profile for each analyte.
To assess the relationship between plasma concentrations of verinurad, allopurinol and the metabolites M1, M8, oxypurinol and dECG variables and HR.	
 Plasma concentrations of verinurad, M1, M8, allopurinol, and oxypurinol and time-matched, baseline-corrected and placebo-adjusted dECG parameters (ΔHR, $\Delta\Delta\text{HR}$, ΔRR interval, $\Delta\Delta\text{RR}$ interval, ΔPR interval, $\Delta\Delta\text{PR}$ interval, ΔQRS interval, $\Delta\Delta\text{QRS}$ interval, ΔQT interval, $\Delta\Delta\text{QT}$ interval, ΔQTcF interval, $\Delta\Delta\text{QTcF}$ interval). Parameters for this outcome measure are the plasma concentration of each analyte at each time point and the time-matched dECG variables HR, RR, PR, QRS, QT and QTcF.
To examine the safety and tolerability of verinurad and allopurinol	
 Assessment of AEs, laboratory variables (haematology, clinical chemistry and urinalysis), vital sign variables (systolic and diastolic blood pressure, pulse rate, body temperature), ECG parameters, telemetry findings and physical examination findings.

See Section 2 for abbreviations.

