- At a time point where more than half of the values are NQ, the gmean, gmean * gSD, gmean - gSD and gCV% will be set to not calculable (NC). The maximum value will be reported from the individual data, and the minimum and median will be set to NQ.
- If all values are NQ at a time point, no descriptive statistics will be calculated for that time point. The gmean, minimum, median and maximum will be reported as NQ and the gCV% and gmean /* gSD as NC.
- The number of values below LLOQ ($n < \text{LLOQ}$) will be reported for each time point together with the total number of collected values (n).

Three observations $> \text{LLOQ}$ are required as a minimum for a plasma concentration to be summarised. Two values $> \text{LLOQ}$ are presented as a minimum and maximum with the other summary statistics as NC.

All reportable plasma PK parameters will be listed for each subject, analyte, and treatment. A separate listing will be provided for the diagnostic PK parameters.

Plasma PK parameters will be summarised for the PK Analysis Set by analyte and treatment using the following descriptive statistics:

- C_{max} , AUC, and AUC_{0-t}: present n, gmean, gmean * gSD, gmean / gSD, arithmetic mean, arithmetic SD, gCV(%), median, min and max.
- $t_{1/2\lambda z}$, CL/F, V_z/F , V_{ss}/F and /MRT: present n, gmean, gmean * gSD, gmean / gSD, arithmetic mean, arithmetic SD, gCV(%), median, min and max.
- t_{max} , t_{lag} , and t_{last} : present n, median, min and max.
- Diagnostic parameters (eg, λz , t upper, t lower, λzN , Rsq-adj and %AUC_{extr}): listed only and not summarised.

Three values are required as a minimum for PK parameters to be summarised. Two values are presented as a min and max with the other summary statistics as NC.

If one or more values for a given parameter is zero (or imputed with zero), then no geometric statistics will be calculated for that parameter and the results for geometric statistics will be set to NA (not applicable).

Pharmacokinetic parameter listings will be presented according to the following rules:

- C_{max} : present to the same number of significant figures as received from the bioanalytical laboratory
- t_{max} , t_{lag} , t_{last} , t lower and t upper time limit: present as received in the data, usually to 2 decimal places
- AUC, AUC_{0-t}, $t_{1/2}$, λ_z , CL/F, Vz/F, Vss/F, MRT, λ_z , %AUC_{extr}, Rsq-adj: present to 3 significant figures
- n and $\lambda_z N$: present as an integer (no decimals)

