12.10.4. Statistical Analysis of Pharmacokinetic Data

No inferential statistical analysis of PK parameters will be conducted.

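### Vss/F is planned as CL/F times MRT from oral-only data, so input time is counted as residence time and the reported volume is too large, by more for ER8 than for IR if bioavailability is equal

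*Combined protocol and SAP*

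**What the plan says.** Section 12.10.2 derives the parameters by non-compartmental methods. It states "Apparent clearance (CL/F) will be determined from the ratio of dose/AUC", and that Vss/F "will be determined by multiplying CL/F by MRT". It gives no formula for MRT and no step that removes absorption or release time.

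Section 12.10.1 describes MRT as "Mean residence time of the unchanged drug in the systemic circulation from zero to infinity". The abbreviation list in Section 2 says the same.

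Dosing is oral throughout. Section 5.3.2 describes a "single oral dose of verinurad 24 mg ER8 formulation (therapeutic exposure) or verinurad 40 mg IR formulation (supra-therapeutic exposure"), each with oral allopurinol, against placebo. There is no intravenous arm.

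MRT and Vss/F are named outcome measures in the synopsis and in Table 6-2, under the secondary objective "To assess the PK of verinurad and its metabolites (M1 and M8) and allopurinol and its metabolite (oxypurinol) in healthy subjects". Section 12.10.3 says "Plasma PK parameters will be summarised for the PK Analysis Set by analyte and treatment", so ER8 and IR values of Vss/F from the same subjects will appear separately. Section 12.10.4 adds "No inferential statistical analysis of PK parameters will be conducted".

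**The concern.** After an intravenous bolus, AUMC/AUC is the mean time a molecule spends in the body, and clearance times that time is Vss. After an oral dose, AUMC/AUC also contains the time taken to release and absorb the drug. The planned product is then no longer a distribution volume; part of it measures how slowly the capsule delivers.

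The point has some weight here because the two active treatments are an extended-release and an immediate-release form of the same drug. Their input times should differ, so the error differs between two results reported under one parameter name. A reader of the study report could take a formulation effect for a difference in distribution. The text cannot be rescued by reading MRT as Section 12.10.1 words it, because oral-only non-compartmental data do not yield that quantity.

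**Working it through.** The plan states no MRT, MAT, Vss/F or ER8/IR volume ratio, so there is no figure of its own to reproduce.

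**Inputs from the protocol**
- IR 40 mg in healthy subjects: Cmax 760 ng/mL, AUC 1270 ng*h/mL, with Cmax described as 10-fold above worst-case clinical exposure (Section 5.4).
- Terminal half-life 13 h with normal renal function; ER8 Cmax at 4 h (Section 5.2.1.3).
- PK samples pre-dose, then at 0.5, 1, 1.5, 2, 3, 4, 5, 6, 8, 12, 24, 36 and 48 h (Table 5-2).

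**Identity**
- MRT_oral = AUMC/AUC = MRT_iv + MAT.
- CL/F x MRT_oral = (CL/F x MRT_iv) + (CL/F x MAT) = Vss/F + (CL/F x MAT).
- With equal F, the ER8/IR ratio of reported Vss/F = (MRT_iv + MAT_ER8) / (MRT_iv + MAT_IR). It exceeds 1 whenever MAT_ER8 > MAT_IR.

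**Size of the excess**
- CL/F (IR) = 40 mg / 1270 ng*h/mL = 31.5 L/h, so each hour of MAT adds about 31.5 L. This step needs no compartmental model.

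**Which disposition shape fits the stated figures**
- One compartment with a 13 h half-life: MRT_iv = 13/ln 2 = 18.8 h. The ER8/IR ratio would be only about 1.0 to 1.6 for MAT_ER8 of 1 to 12 h. But this model needs AUC/Cmax of at least 18.8 h, and Section 5.4 gives 1270/760 = 1.67 h, about 11 times less. It conflicts with the protocol's figures if the 13 h applies to IR.
- Two compartments with terminal half-life 13 h, fitted to AUC/Cmax = 1.67 h, with 5 to 40% of AUC in the terminal phase and IR absorption rate 1.5 to 4 /h (both assumed): MRT_iv is about 1.4 to 7.8 h.

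**ER8/IR ratio, two-compartment case**

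| Assumption about ER8 | Ratio |
|---|---|
| MAT 2 to 12 h, first- or zero-order input, exact | 1.2 to 6.5 |
| Same, non-compartmental on the planned sampling times | 0.9 to 5.7 |
| Cmax about 76 ng/mL and dose-proportional AUC, exact | about 1.4 to 4.6 |

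The last row assumes ER8 Cmax = 760/10 = 76 ng/mL and AUC = 1270 x 24/40 = 762 ng*h/mL, so AUC/Cmax is about 10 h.

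**Three cases to show the arithmetic**
- MRT_iv 7.59 h, MAT_IR 1/1.5 = 0.67 h, MAT_ER8 4 h: 11.59/8.25 = 1.40.
- MRT_iv 6.09 h, MAT_IR 1/4 = 0.25 h, MAT_ER8 6 h: 12.09/6.34 = 1.91. In litres at 31.5 L/h: correct value 31.5 x 6.09 = 192 L, IR reported 31.5 x 6.34 = 200 L, ER8 reported 31.5 x 12.09 = 381 L.
- MRT_iv 1.4 h, MAT_IR 0.67 h, MAT_ER8 8 h: 9.4/2.07 = 4.5.

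Ratios below 1 on the sampling times come from the grid and not from the identity. In the lowest case the exact ratio is 1.16, but the modelled IR peak at 0.28 h falls before the first post-dose sample at 0.5 h, and the estimated ratio is 0.90.

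**The case against.** **No trial conclusion rests on this.** That stands. The primary model in Section 12.9 uses verinurad plasma concentrations and QTcF, not MRT or Vss/F. PK is descriptive, and no objective compares the two formulations.

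**The size depends on assumptions.** That stands too. A reader might infer that verinurad will appear to have a volume a definite 2 to 4 times larger after ER8. The documents do not support that: they give no MRT, MAT, IR tmax, ER8 AUC or relative bioavailability, and Section 5.2.1.3 refers to the Investigator's Brochure for the IR parameters. The 13 h half-life is in a paragraph that opens with the ER8 capsule and is not tied to IR.

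**An apparent volume can differ by formulation.** A reader might infer that any ER8/IR difference in Vss/F must be an artefact. It need not be: Vss/F contains F, and if F differs, so does Vss/F, even with a perfect MRT.

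**Metabolites.** A reader might infer that Vss/F is also wrong for M1, M8 and oxypurinol. Sections 2 and 12.10.1 limit CL/F to the parent drug, so the planned product cannot be formed for them. Only MRT, if reported for metabolites, is concerned; it would then include formation time as well.

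**Vz/F as a substitute.** It is tempting to let Vz/F take the place of Vss/F. On these figures Vz/F = 31.5 x 13/ln 2 = about 591 L. It is a different parameter, not a corrected Vss/F.

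**Existing safeguards.** Section 12.10.2 flags MRT and Vss/F for possible exclusion when the terminal fit spans fewer than 3 half-lives (3 x 13 = 39 h within 48 h of sampling). That may remove some values, but it concerns the precision of the terminal slope and does not address input time. Section 12.1 allows changes through the study report or an abbreviated SAP, which makes the correction easy without making it unnecessary.

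**Conclusion.** Wrong as written, low severity. The plan applies an intravenous relation to oral data, so MRT will not be what Section 12.10.1 says it is, and Vss/F will exceed its proper value by (CL/F) x MAT. This rests on MRT being the usual AUMC/AUC. The plan does not say so, but no other route to MRT is described and there is no intravenous arm.

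The excess is about 31.5 L per hour of MAT at the IR clearance. It is larger for ER8 than for IR if F is equal and ER8 input is slower. The ratio between them remains open within the ranges shown. Allopurinol is given as the same tablet in both active treatments, so its Vss/F is overstated too, but without a formulation contrast.

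**What to change.** - Drop Vss/F for the oral treatments from the synopsis, Table 6-2 and Sections 12.10.1 to 12.10.3. At minimum, state that it is CL/F times oral MRT including absorption, that it is not a disposition volume, and that it is not for comparison between ER8 and IR.
- Define MRT in Sections 2 and 12.10.1 as oral AUMC/AUC including absorption time, and formation time if it is reported for metabolites.
- Leave Vz/F as already planned, as a separate parameter.

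Subtracting MAT is not an option, because the planned data do not provide it. The cost is wording in the protocol or an abbreviated SAP and, at most, one derived parameter fewer. No samples, visits or subjects are affected.

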12.10.3. Presentation of Pharmacokinetic Data

A listing of PK blood sample collection times, as well as derived sampling time deviations will be provided. Plasma concentrations will be summarised for the PK Analysis Set for each time point by analyte and treatment using the following descriptive statistics: n, n below LLOQ, geometric mean (gmean), geometric coefficient of variation [CV] (gCV%), arithmetic mean, arithmetic SD, gmean /* geometric SD (gSD) (gmean / gSD and gmean * gSD), median, minimum (min) and maximum (max).

The gmean is calculated as the exponential(μ) where μ is the arithmetic mean calculated using log-transformed data.

The gCV% is calculated as $100 * \sqrt{\exp(s^2) - 1}$ where s is the SD of the log-transformed data.

The gmean /* gSD are calculated as $\exp[\mu \pm s]$.

Pharmacokinetic concentration data will be presented in the listings to the same number of significant figures as the data received from the bioanalytical laboratory (usually to 3 significant figures) and against the same units as received. Pharmacokinetic concentration descriptive statistics will all be presented to 4 significant figures with the exception of the min and max which will be presented to 3 significant figures and n and n < LLOQ which will be presented as integers.

Individual concentrations with time deviations of greater than $\pm 10\%$ from the protocol scheduled time will be used in the PK analysis but will be flagged for exclusion from the summary tables and corresponding figures.

Plasma concentrations that are NQ, Not Reportable or missing will be handled as follows:

Individual concentrations below the LLOQ of the bioanalytical assay will be reported as NQ in the listings with the LLOQ defined in the footnotes of the relevant tables, figures and listings. Individual plasma concentrations that are Not Reportable will be reported as no result (NR) and those that are missing will be reported as NS (No Sample) in the listings. Plasma concentrations that are NQ, NR or NS will be handled as follows for the provision of descriptive statistics:

- Any values reported as NR or NS will be excluded from the summary tables and corresponding figures.
- At a time point where less than or equal to 50% of the concentration values are NQ, all NQ values will be set to the LLOQ, and all descriptive statistics will be calculated accordingly.
- At a time point where more than half of the values are NQ, the gmean, gmean * gSD, gmean - gSD and gCV% will be set to not calculable (NC). The maximum value will be reported from the individual data, and the minimum and median will be set to NQ.
- If all values are NQ at a time point, no descriptive statistics will be calculated for that time point. The gmean, minimum, median and maximum will be reported as NQ and the gCV% and gmean /* gSD as NC.
- The number of values below LLOQ ($n < \text{LLOQ}$) will be reported for each time point together with the total number of collected values (n).

Three observations $> \text{LLOQ}$ are required as a minimum for a plasma concentration to be summarised. Two values $> \text{LLOQ}$ are presented as a minimum and maximum with the other summary statistics as NC.

All reportable plasma PK parameters will be listed for each subject, analyte, and treatment. A separate listing will be provided for the diagnostic PK parameters.

Plasma PK parameters will be summarised for the PK Analysis Set by analyte and treatment using the following descriptive statistics:

- C_{max} , AUC, and AUC_{0-t}: present n, gmean, gmean * gSD, gmean / gSD, arithmetic mean, arithmetic SD, gCV(%), median, min and max.
- $t_{1/2\lambda z}$, CL/F, V_z/F , V_{ss}/F and /MRT: present n, gmean, gmean * gSD, gmean / gSD, arithmetic mean, arithmetic SD, gCV(%), median, min and max.
- t_{max} , t_{lag} , and t_{last} : present n, median, min and max.
- Diagnostic parameters (eg, λz , t upper, t lower, λzN , Rsq-adj and %AUC_{extr}): listed only and not summarised.

Three values are required as a minimum for PK parameters to be summarised. Two values are presented as a min and max with the other summary statistics as NC.

If one or more values for a given parameter is zero (or imputed with zero), then no geometric statistics will be calculated for that parameter and the results for geometric statistics will be set to NA (not applicable).

Pharmacokinetic parameter listings will be presented according to the following rules:

- C_{max} : present to the same number of significant figures as received from the bioanalytical laboratory
- t_{max} , t_{lag} , t_{last} , t lower and t upper time limit: present as received in the data, usually to 2 decimal places
- AUC, AUC_{0-t}, $t_{1/2}$, λ_z , CL/F, Vz/F, Vss/F, MRT, λ_z , %AUC_{extr}, Rsq-adj: present to 3 significant figures
- n and $\lambda_z N$: present as an integer (no decimals)

The descriptive statistics for PK parameter data will all be presented to 4 significant figures with the exception of the min and max which will be presented to 3 significant figures apart from the following:

- t_{max} , t_{lag} , and t_{last} : present as received in the data, usually to 2 decimal places.

Pharmacokinetic data (concentrations and parameters) from subjects excluded from the PK Analysis Set will be included in the data listings, but not in the descriptive statistics, as appropriate.

Individual subject plasma concentrations versus actual time will be plotted for each analyte in linear and semi-logarithmic scale with all treatments overlaid on the same plot and separate plots for each subject.

Combined individual subject plasma concentration versus actual times will be plotted in linear and semi-logarithmic scale. Separate plots will be presented for each analyte and treatment.

Geometric mean plasma concentration ($/*$ gSD) versus nominal sampling time will be plotted in linear and semi-logarithmic (no SD presented) scale for each analyte with all treatments overlaid on the same figure.

All gmean plots or combined plots showing all subjects by analyte and treatment will be based on the PK Analysis Set. Individual plots by subject will be based on the Safety Analysis Set.

For consistency, the plasma concentration values used in the gmean data graphs will be those given in the descriptive statistics summary table for each time point.

For gmean concentration-time plots, NQ values will be handled as described for the descriptive statistics; if the geometric mean is NQ, the value plotted will be zero for linear plots and missing for semi-logarithmic plots. Any gmean $/*$ gSD error bar values that are negative will be truncated at zero on linear concentration-time plots and omitted from semi-logarithmic plots.

For individual plots, plasma concentrations which are NQ prior to the first quantifiable concentration will be set to a value of zero (linear plots only). After the first quantifiable concentration, any NQ plasma concentrations will be regarded as missing.

